5. STUDY CONDUCT

5.1 Subject enrollment, randomization, and initiation of investigational product

According to the study protocol, patients who are referred for coronary angiography or NSTEMI-ACS may be screened for randomization. Subjects meeting the inclusion and none of the exclusion criteria will be evaluated and their demographic, medical history and current clinical characteristics will be recorded.

During the screening period the eligibility check and physical examination will be performed with assessment of vital signs (heart rate and blood pressure measurement). During the screening period obtained local laboratory results should be examined for exclusion criteria (eGFR, HAS-BLED score, cardiac troponin). The subject will then be informed about the study and will sign the Informed Consent Form.

Day 1 of the study is defined as the day of randomization to ticagrelor versus clopidogrel. This should be chosen by the investigator to be the day before the scheduled PCI procedure.

Day 2 of the study is defined as the day of randomization to RIPC or control and subsequent (within 1 hour) coronary angiography and PCI.

In patients already treated with clopidogrel for 3 to 7 days, actions performed on Day 1 and Day 2 may be combined into a single day provided that;

- a. Twenty-four hours have elapsed between the last dose of clopidogrel and the randomization to the ticagrelor or clopidogrel group, and
- b. There is sufficient time (2-4 hours) between the randomization and subsequent intake of clopidogrel or ticagrelor and the 2nd randomization to the RIPC or control group.

In these case patients are 1:1 randomized to ticagrelor or clopidogrel, and undergo the second randomization within 2-4 hours

If for unforeseen reasons, PCI is not conducted within the prespecified timeframe the patient should be withdrawn from the study.

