6.4.6 ECG

6.4.6.1 Resting 12-lead ECG

On Day 1 and Day 2. Furthermore, whenever it is considered appropriate according to symptoms and physical findings. Particular inspection for bradycardia, conduction disturbances, ventricular pauses.

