11. EVALUATION AND CALCULATION OF VARIABLES

11.1 Calculation or derivation of efficacy variable(s)

The primary efficacy variable, cardiac troponin I at 24 hours post-PCI will be determined according to local standard clinical practice. In detail, cTnI will be analyzed with an automated immunoassay (Bayer ADVIA IMS Troponin-I Ultra method, Bayer, Berlin, Germany). The 99th percentile of the cTnI level in a reference population (upper reference, limit, URL) of healthy volunteers was below the lower limit of detection of 0.04 ng/mL. The coefficient of variation (CV) of the assay was <10%, complying with the recommendations of the European Society of Cardiology (ESC)/ American College of Cardiology (ACC)/ American Heart Association (AHA) for optimal precision. The analytical range was 0.01 to 50ng/mL, with an assay sensitivity of 0.006 ng/mL.

Chest pain during PCI is a secondary efficacy variable. It will be assessed during the post-PCI clinical examination of the subject by the investigator or by an appropriately qualified person to whom the investigator has delegated this duty. A numerical 10 point scale will be used (0: no pain, 10: most severe discomfort ever experienced).

ST-segment deviation during balloon occlusion will be monitored as a secondary efficacy variable. It will be defined as the absolute value of ST-segment deviation at 60-80ms after the J-point in mm at the beginning of coronary angiography minus ST-segment deviation at 60-80ms after the J-point in mm during balloon occlusion.

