12.2 Methods of statistical analyses

The efficacy analysis will be performed in the population of subjects valid for safety analysis.

The statistical assessment of the primary outcome measure (post-procedural cTnI) will be performed using ANCOVA (analysis of covariance), with post-procedural cTnI as a dependent variable, -ticagrelor/clopidogrel treatment and –RIPC/no RIPC as fixed factors and pre-procedural cTnI as a covariate. If not mentioned otherwise, all statistical tests will be performed tow-sided with a type I error rate of 5% and 95% confidence intervals (two-sided) will be given.

The statistical assessment of the secondary outcome measures (pain score, and ST-segment deviation) will be performed using ANOVA (analysis of variance). The ANOVA tests the null hypothesis that samples in two or more groups are drawn from populations with the same mean values. If the ANOVA test is statistically significant, pairwise comparison of subgroups will be performed with the Tukey-Kramer test. If not mentioned otherwise, all statistical tests will be performed tow-sided with a type I error rate of 5% and 95% confidence intervals (two-sided) will be given.

The safety analysis will be performed in the population of subjects valid for safety analysis.

The incidence of the composite of major and non-major bleeding according to the TIMI criteria and the incidence of major bleeding will be tabulated and further analyzed using Fisher's exact test. Fisher's exact test is a significance test for a 2x2 table. This test evaluates all distribution probabilities for a 2 x 2 table and produces an exact probability for a given set of observed frequencies. The null hypothesis is that the row and column variables are unrelated, or that there is no difference in the respective proportions. If not mentioned otherwise, all statistical tests will be performed two-sided with a type I error rate of 5% and 95% confidence intervals (two-sided) will be given.

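### ST-segment deviation is a change score tested by ANOVA with no baseline covariate; this is valid but may lose precision, and a baseline ST value could be adjusted for at almost no cost

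*Combined protocol and SAP*

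**What the plan says.** Section 11.1 (repeated in 6.2 and 6.3.1) makes ST-segment deviation during balloon occlusion a secondary efficacy variable and defines it as the "absolute value of ST-segment deviation at 60-80ms after the J-point in mm at the beginning of coronary angiography minus ST-segment deviation" during occlusion. The starting ST value must therefore be measured in every patient who contributes to the outcome.

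Section 12.2 gives the test: "The statistical assessment of the secondary outcome measures (pain score, and ST-segment deviation) will be performed using ANOVA (analysis of variance"), followed by Tukey-Kramer pairwise comparisons if the ANOVA is significant. No covariate is named. For the primary outcome the same section specifies ANCOVA with "pre-procedural cTnI as a covariate".

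Two points on timing matter. The starting ST value is taken on Day 2, which section 5.1 defines as the day of "randomization to RIPC or control and subsequent (within 1 hour) coronary angiography and PCI", so it follows both randomisations. Section 6.4.6.1 schedules a resting 12-lead ECG "On Day 1 and Day 2". Section 6.2 lists the Day 1 trace under screening and the Day 2 trace after the procedure.

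**The concern.** A change score fixes the weight of the baseline at 1 whatever the data show, whereas ANCOVA estimates that weight. If the slope of occlusion ST on starting ST differs from 1, the change score still carries baseline variation that a covariate would remove. Intervals are then wider than the data require, and a chance difference between arms in starting ST shifts the estimate.

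The plan applies baseline adjustment to cTnI and relies on it in the sample size (section 12.3 uses a baseline correlation of 0.7 and cites an ANCOVA sample-size formula). It gives no reason for omitting it from the one secondary outcome that is built on a baseline. ST deviation is one of only two secondary efficacy outcomes.

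**Working it through.** **Plan's own figure.** There is none for ST: no SD, correlation, effect size or power is stated. Section 12.3 sizes the trial on cTnI alone. Its 152 can be reproduced with the adjusted SD 0.20 × √(1 − 0.7²) = 0.1428 and the 0.14 versus 0.24 ng/mL contrast: 2 × (0.1428 × (1.960 + 0.842)/0.10)² = 32.02 per cell; 32.02/0.85 = 37.67, rounded up to 38; 4 × 38 = 152. This shows only that the plan takes credit for baseline adjustment of cTnI. Patients expected to be evaluable: 152 × 0.85 = 129.2.

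**Notation.** A is ST at the start of angiography and B is ST during occlusion. k = SD(A)/SD(B), ρ is their correlation, and the slope of B on A is ρ/k. All values of k and ρ below are assumptions.

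**Signed change, adjusted for A.** In units of Var(B), Var(A − B) = 1 + k² − 2ρk, and the residual variance after adjustment is 1 − ρ². The excess variance of the unadjusted change score is therefore (k − ρ)²/(1 − ρ²). Equivalent patients lost = 129.2 × (1 − 1/(1 + excess)).

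| k | ρ | slope | excess variance | equivalent patients lost |
|---|---|---|---|---|
| 0.5 | 0 | 0 | 25% | 26 |
| 0.5 | 0.2 | 0.4 | 9% | 11 |
| 0.5 | 0.3 | 0.6 | 4% | 5 |
| 0.5 | 0.5 | 1.0 | 0% | 0 |
| 0.25 | 0 | 0 | 6% | 8 |
| 0.25 | 0.15 | 0.6 | 1% | 1 |
| 0.25 | 0.6 | 2.4 | 19% | 21 |

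With k = 1 the excess would be larger (54% at ρ = 0.3, 18% at ρ = 0.7, 5% at ρ = 0.9). That requires resting ST to vary as widely as ST under occlusion, which nothing in the documents supports.

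**Imbalance.** If the arms differ by d in A, the expected shift in the mean of A − B is (1 − slope) × d: 0 at slope 1, 0.4d at slope 0.6, and d at slope 0.

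**Unsigned change |A − B|.** Simulation with SD(A) 0.5 mm and an occlusion shift of mean 1.5 mm and SD 1 mm, adjusting for A and |A|, with the slope falling from 0.3 to 0:
- all shifts in one direction: excess variance 11% to 21%;
- 90% of shifts in one direction: 7% to 13%;
- elevation and depression equally common: about 0%.

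**Day 1 ECG as covariate.** The figures above are for adjustment by A itself. If the Day 1 value relates to the change only through A, the share of variance removed is multiplied by its squared correlation with A. A 25% excess means that A removes 1 − 1/1.25 = 20% of the variance. If the Day 1 value correlated 0.7 with A (a value chosen only for illustration), it would remove 0.20 × 0.49 = 9.8%, an excess of 1/(1 − 0.098) − 1 = 11%.

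**Cost.** With about 129 patients, four cells and one covariate, there are 129 − 5 = 124 residual degrees of freedom. Each covariate costs about 1/124 = 0.8% of variance.

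**The case against.** ANOVA on a prespecified change score is unbiased under randomisation and needs no assumption about starting ST, because the change is itself the outcome. No power is claimed for ST. The larger figures need strong inputs: 25% needs starting ST to say nothing about ST later in the same procedure, and 19% needs each 1 mm at rest to predict 2.4 mm at occlusion. If occlusion simply adds a shift unrelated to starting ST, the slope is 1 and nothing is lost. All of this stands. It rules out the flat statement that precision is lost, and it rules out reading 26 of 129 patients as a wasted share of this trial.

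A reader might also infer that adjusting for starting ST carries no risk, because the change score already subtracts it. The documents do not support that. The value follows both randomisations, the first antiplatelet dose and, where allocated, RIPC. A difference between arms in it need not be chance, and conditioning on it assumes that treatment does not affect resting ST. This alters the choice of covariate but not the case for having one, since a screening ECG is already scheduled. The plan also accepts a similar position for cTnI: if its pre-procedural value is the one in the Day 2 pre-procedural assessment, it follows the first randomisation on the standard path.

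Enrolment of NSTEMI-ACS patients does not show that resting ST varies materially. The documents give no resting ST data, stable CAD is also named in sections 4 and 6.2, and section 4.2 excludes patients whose baseline cTnI is rising or markedly raised.

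**Conclusion.** The point holds as an efficiency improvement to a secondary outcome. Section 12.2 omits a baseline covariate for an outcome derived from a baseline, and this may cost precision and leave (1 − slope) times any chance imbalance in the estimate. The size cannot be fixed from the documents. Under the stated assumptions the excess variance runs from 0% (slope 1, or an unsigned outcome with evenly mixed shifts), through about 4-9% at slopes of 0.6 to 0.4 with k = 0.5, to about 25% at k = 0.5 with no correlation. These figures assume adjustment for the start-of-angiography value; a Day 1 covariate would recover less to the extent that it tracks that value imperfectly. It would be wrong to infer that the planned test is invalid or biased on average, because randomisation protects it.

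**What to change.** 1. In 11.1, state whether the outcome is the signed difference, the absolute value of the whole difference, or the absolute starting value minus the occlusion value. The present wording allows more than one reading.
2. In 12.2, analyse that variable by ANCOVA with the randomised factors and baseline ST deviation as covariate, and make any pairwise comparisons on the adjusted means. If the outcome is unsigned, also enter the absolute baseline value.
3. Use ST from the Day 1 screening ECG as the main covariate. Specify that it is the trace recorded before the first randomisation, including in patients whose Day 1 and Day 2 are combined.
4. Repeat the analysis with the start-of-angiography value as a sensitivity analysis, stating that it assumes treatment does not affect resting ST.

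Cost: one or two degrees of freedom (under 1% of variance each) and a short edit to 11.1 and 12.2. No extra ECG is needed, but someone must read ST from the Day 1 trace. The plan does not currently ask for that, nor does it name a lead. The measurement point and lead should match those of the outcome, and the two blinded assessors in 5.3 are the natural readers.

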2.3 Safety objective

Safety monitoring will be performed daily during the index hospitalization. The presence of adverse events will be assessed by history, detailed physical examination and appropriate laboratory tests that will be described in the protocol accordingly.

In addition patients will be instructed to contact the study personnel in case of any emergency situation whereas an adverse event reporting system will be available throughout the study.

In detail, bleeding according to the Thrombolysis in Myocardial Infarction (TIMI) bleeding criteria will be recorded and assessed throughout study duration. According to these criteria bleeding is defined as follows:

Non-CABG Related Bleeding:

1. Major

- Any intracranial bleeding (excluding microhemorrhages <10 mm evident only on gradient-echo MRI)
- Clinically overt signs of hemorrhage associated with a drop in hemoglobin of ≥ 5 g/dL or a $\geq 15\%$ absolute decrease in haematocrit
- Fatal bleeding (bleeding that directly results in death within 7 d)

2. Minor

- Clinically overt (including imaging), resulting in hemoglobin drop of 3 to <5 g/dL or $\geq 10\%$ decrease in haematocrit
- No observed blood loss: ≥ 4 g/dL decrease in the haemoglobin concentration or $\geq 12\%$ decrease in haematocrit

- Any overt sign of hemorrhage that meets one of the following criteria and does not meet criteria for a major or minor bleeding event, as defined above
- Requiring intervention (medical practitioner-guided medical or surgical treatment to stop or treat bleeding, including temporarily or permanently discontinuing or changing the dose of a medication or study drug)
- Leading to or prolonging hospitalization
- Prompting evaluation (leading to an unscheduled visit to a healthcare professional and diagnostic testing, either laboratory or imaging)

3. Minimal

- Any overt bleeding event that does not meet the criteria above
- Any clinically overt sign of haemorrhage (including imaging) associated with a <3 g/dL decrease in haemoglobin concentration or <9% decrease in haematocrit

Bleeding in the Setting of CABG:

- Fatal bleeding (bleeding that directly results in death)
- Perioperative intracranial bleeding
- Reoperation after closure of the sternotomy incision for the purpose of controlling bleeding
- Transfusion of ≥ 5 U PRBCs or whole blood within a 48-h period; cell saver transfusion will not be counted in calculations of blood products.
- Chest tube output >2 L within a 24-h period

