3. STUDY PLAN AND PROCEDURES

3.1 Overall study design and flow chart

The TRIP study will be a randomized, assessor-blind, active comparator-controlled, clinical trial using a 2×2 factorial design, with 1:1 patient allocation to ticagrelor or clopidogrel and within each treatment a 1:1 allocation to RIPC or control.

According to the study plan, patients who are referred for coronary angiography or NSTEMI-ACS may be screened for randomization.

	Day 1/ Screening	Day 2	Day 3	Day 30 (±5days)
Informed consent form	x			
Inclusion criteria	x			
Exclusion criteria	x	x	x	

Medical history	X			X
Concomitant disease	X			X
Concomitant medication	X	X	X	X
Physical examination (vital signs)	X	X	X	X
ECG	X	X		
Local laboratory values	X	X	X	
Randomization	X	X		
Treatment initiation	X			
RIPC		X		
Coronary angiography assessment		X		
PCI		X		

[figure not shown]
Day 1 of the study is defined as the day of randomization to ticagrelor versus clopidogrel. This should be chosen by the investigator to be the day before the scheduled PCI procedure.

Day 2 of the study is defined as the day of randomization to RIPC or control and subsequent (within 1 hour) coronary angiography and PCI.

In patients already treated with clopidogrel for 3 to 7 days, actions performed on Day 1 and Day 2 may be combined into a single day provided that;

- a. Twenty four hours have elapsed between the last dose of clopidogrel and the randomization to the ticagrelor or clopidogrel group, and
- b. There is sufficient time (2-4 hours) between the randomization and subsequent intake of clopidogrel or ticagrelor and the 2nd randomization to the RIPC or control group.

If for unforeseen reasons, PCI is not conducted within the prespecified timeframe the patient should be withdrawn from the study.

* In case of a patient already on clopidogrel for 3-7 days, ticagrelor loading dose is administered on the day of the procedure (24 hours after the last clopidogrel dose), and no 2nd ticagrelor dose is administered. ** In case of a patient already on clopidogrel for 3-7 days, no loading dose of clopidogrel is administered, but the patient ideally receives 75mg clopidogrel 2-3 hours before the procedure.

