11.2 Calculation or derivation of safety variable(s)

The frequency of bleeding according the TIMI criteria will be recorded.

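### Fisher's exact test for TIMI bleeding runs at no more than 3.7% against the stated 5%; Boschloo's exact test on the same 2x2 tables would recover about 2 to 7 points of power for any bleeding

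*Combined protocol and SAP*

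**What the plan says.** Section 2.3 (Safety objective) says that "bleeding according to the Thrombolysis in Myocardial Infarction (TIMI) bleeding criteria will be recorded and assessed throughout study duration" and defines major, minor and minimal grades for bleeding not related to CABG. The lowest grade takes in "Any overt bleeding event that does not meet the criteria above", so major plus non-major bleeding amounts to any bleeding. Section 11.2 adds only this: "The frequency of bleeding according the TIMI criteria will be recorded".

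Section 12.2 sets the analysis: "The incidence of the composite of major and non-major bleeding according to the TIMI criteria and the incidence of major bleeding will be tabulated". Both endpoints are then to be tested by Fisher's method, which the section describes in these words: "This test evaluates all distribution probabilities for a 2 x 2 table and produces an exact probability for a given set of observed frequencies". On level and sidedness, "all statistical tests will be performed two-sided with a type I error rate of 5" per cent, and two-sided 95% intervals are promised in general terms. No effect measure for bleeding is named.

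The section does not say which two groups form the table. Section 3.1 describes four cells, with "1:1 patient allocation to ticagrelor or clopidogrel and within each treatment a 1:1 allocation to RIPC or control", so the drug margin, the RIPC margin or pairs of cells are all possible. No bleeding rate, effect size or power for bleeding appears anywhere. The 152 patients in section 12.3 rest on troponin.

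**The concern.** Section 1.4 names bleeding as the risk of giving stable patients the more potent drug, and it is the only safety outcome with a planned test. Fisher's test conditions on the total number of events. With few events its attainable levels are coarse, and its true error rate falls well below the nominal one. The level given up buys no protection that the plan asks for, and it lowers the chance of detecting a real excess. A non-significant result could then be taken as reassurance when the test had little chance of showing a difference. Because the comparison is unnamed, the choice of rows could also be made after the data are seen.

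**Working it through.** **Inputs.**
- 152 patients, 38 per cell (section 12.3), give 2 x 38 = 76 per drug arm.
- The safety set needs one dose only (section 12.1.2), so close to 76 per arm is reasonable. If all of the 15% dropout lacked bleeding data, 0.85 x 76 = 64.6, about 65 per arm.
- The level is two-sided 5% (section 12.2).
- Assumed, because the plan gives no rates: any bleeding on clopidogrel p = 5-30%, odds ratio (OR) 1.5 to 3. The ticagrelor rate is q = OR x p / (1 - p + OR x p).

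The plan has no bleeding figure to reproduce.

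**Step 1: true level of Fisher's test.** For all 77 x 77 tables (a, b), compute the two-sided Fisher p-value. With rejection region R, the error rate at a common rate p is the sum over R of Bin(a; 76, p) x Bin(b; 76, p). With R = {Fisher p <= 0.05}, the maximum over p is 3.66%. At common rates of 5, 10, 20 and 30% it is 1.5, 2.7, 3.1 and 3.3%.

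**Step 2: Boschloo's test.** It uses the Fisher p-value as its statistic and takes the largest cut-off whose maximum error rate stays within 5%. At 76 v 76 that cut-off is Fisher p <= 0.0685, with maximum error rate 4.92%. The next attainable cut-off, 0.0691, gives 5.07% and is too large. Because 0.0685 exceeds 0.05, every table rejected by Fisher's test is also rejected by Boschloo's, so power cannot be lower.

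**Step 3: power for any bleeding.** Power is the sum over R of Bin(a; 76, q) x Bin(b; 76, p), by full enumeration. Each entry is Fisher / Boschloo, in per cent:

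| Clopidogrel rate | OR 1.5 | OR 2 | OR 2.5 | OR 3 |
|---|---|---|---|---|
| 5% | 4.0 / 6.6 | 11.0 / 14.9 | 22.0 / 26.9 | 35.4 / 40.7 |
| 10% | 8.5 / 10.8 | 23.2 / 28.3 | 42.8 / 49.4 | 61.8 / 68.0 |
| 15% | 11.2 / 14.6 | 32.3 / 37.8 | 56.8 / 62.4 | 76.0 / 80.2 |
| 20% | 13.9 / 17.3 | 39.4 / 44.9 | 65.3 / 70.3 | 82.8 / 86.3 |
| 30% | 17.5 / 21.6 | 48.5 / 53.5 | 74.4 / 77.5 | 88.6 / 90.3 |

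The gain runs from 1.7 points (30%, OR 3) to 6.7 points (10%, OR 2.5). With 65 per arm the maximum levels are 3.5% and 4.9%, and the gain is 1.9 to 6.9 points.

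**Step 4: major bleeding.** For k v 0 events the two-sided Fisher p is 2 x C(76, k) / C(152, k).
- k = 5: 2 x (76 x 75 x 74 x 73 x 72) / (152 x 151 x 150 x 149 x 148) = 0.058.
- k = 6: multiply by 71/147, giving 0.028.

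Fisher's test therefore needs at least 6 v 0; with one event on the other arm it needs 8 v 1 (p = 0.034; 7 v 1 gives 0.063). Under Boschloo's test 5 v 0 and 7 v 1 fall inside the cut-off of 0.0685, while 4 v 0 (0.120) does not. The change helps little at low rates: at assumed major-bleeding rates of 2% v 1%, power is 0.2% with Fisher's test and 0.9% with Boschloo's; at 5% v 2% it is 5.2% and 10.4%.

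**The case against.** Fisher's test is valid, familiar and a common choice for sparse safety counts. Conservatism is not an error, the plan claims no power for bleeding, and it already promises tabulated incidences and 95% intervals. All of that stands, which is why this is an improvement and not a defect. It does not remove the point: a test with the same validity and more power is available on the same tables, and the comparison and effect measure are still unnamed.

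Three stronger readings are tempting.

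- **That the plan gives away 5 to 10 points of power.** A reader might infer this from comparing Fisher's test with a Wilcoxon test on the four ordered levels (none, minimal, minor, major). Under a common odds ratio of 2 to 3 that gap is 4 to 10 points, but at odds ratios of 1.2 to 1.5 it is about 2 to 5. The documents give no rates, so no such figure is a property of the plan.
- **That cutting the graded scale is the cause, and an ordinal test should replace the 2x2 tests.** Compared with a chi-square test on the same any/none table, the ordinal test changes power by only -1.5 to +3.1 points at clopidogrel rates up to 30%; most of the gap is Fisher's conservatism. Section 1.4 expects the extra bleeding to be of the milder kind. If the excess is confined to minimal bleeds (30% rate, grades split 65/28/7), the ordinal test falls below Fisher's: 44% v 49% at OR 2, 66% v 74% at OR 2.5 and 81% v 89% at OR 3. Section 2.3 also lists CABG bleeding apart from the three grades, so the ordering would need further rules.
- **That the weak test of major bleeding is a wrong choice of analysis.** It follows from few events among 152 patients. No test rescues it.

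**Conclusion.** The point holds as a minor one. At 76 v 76 Fisher's test has a true two-sided error rate of at most 3.7% against the stated 5%. Boschloo's test reaches 4.9%, stays within the level and is never less powerful. These levels depend only on the arm sizes and on the comparison being by drug, which is inferred.

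The gain of about 2 to 7 points for any bleeding also rests on assumed clopidogrel rates of 5-30% and odds ratios of 1.5 to 3. Even then power is often modest, for example 23% rising to 28% at a 10% rate and OR 2. A non-significant bleeding result would not show the absence of an excess under either test, so the estimate and interval matter more than the p-value.

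**What to change.** In section 12.2:

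1. Name the bleeding comparison as ticagrelor v clopidogrel, pooled over RIPC and control, in the safety set.
2. Replace Fisher's exact test with Boschloo's exact test for both 2x2 tables, with the two-sided Fisher p-value as the ordering statistic.
3. Report any and major bleeding as incidence by arm and risk difference with an exact 95% confidence interval, naming the interval method.
4. State that major bleeding is to be read from the estimate and interval. Give the reason: under the planned Fisher test nothing below 6 v 0 is significant, and the change of test moves that limit only to 5 v 0.
5. If wanted, add an ordinal analysis of each patient's worst TIMI grade as a supplement only, with a rule for placing CABG bleeding.

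The cost is a few lines of text and code; no new data or patients are needed. Boschloo's test is less familiar to readers and may need software other than the SPSS version named in section 12.3.
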